#### 184 **1.5 Delivering the Intervention**

#### 185 A workflow for delivering the STOP intervention is provided in Figure 2.

#### 189 **Randomizing Clinics and Selecting Clinic Launch Dates** 1.5.1 190 We will randomize clinics according to the randomization plan detailed in Section 2.2. 191 1. All clinics were able to start the intervention as early as February 2014. All clinics 192 waited for the EPIC upgrade at the end of April, then started to work on testing the 193 tools in May and June. 194 2. Usual care clinics will have access to the STOP CRC tools on a delayed roll-out beginning 195 August 2015 (decision in Steering committee 2/12/15). 196 1.5.2 Pre-launch period [3-months prior to launch]: 197 a. We will conduct a clinic readiness assessment; we will interview key leadership 198 at the clinics [medical director, operations director, QI lead, and EMR specialist] 199 to learn about current CRC-related practices and clinic attributes. These 200 interviews will be conducted in-person or over the phone. 201 b. We will train clinic staff in data validation activities and Best Practices to 202 improve data quality. Data validation efforts will take place in both intervention 203 and usual care sites. The training will address use of Health Maintenance (HM) 204 to track patient use of preventive services, including CRC screening, and 205 obtaining records from outside facilities. 206 i. Updating HM using existing clinic data: At the beginning of YR01 and 207 YR02, OCHIN will provide clinics with a list of patients in their clinic 208 organization who have evidence of recent CRC screening [colonoscopy 209 in the past 9 years, sigmoidoscopy in the past 4 years, fecal testing in 210 the past 11 months]. Clinic will be encouraged to update HM for these 211 patients and obtain outside records, where needed; 212 ii. Updating HM using claims data: We will provide all clinics with 213 Medicaid claims data for patients assigned to their clinic that have had 214 a recent CRC screening. Clinics will be encouraged to update HM for 215 these patients and obtain outside records, where needed. 216 iii. Use of HM will be compared across intervention and usual care sites, as 217 part of on-going validation activities [see Section 2.8.] 218 c. We will review a readiness checklist that will proactively prepare clinics to 219 address early issues that can arise during launch. 220 i. The readiness checklist will contain sections on 1) assuring lab 221 interfaces are in place; 2) assessing needs for intervention materials; 3) 222 establishing a site-specific training plan. 223 ii. The checklist will be reviewed with each clinic during a pre-launch 224 phone call with the project director, [name], the EMR 225 specialist from Virginia Garcia, and [name] from Lean HealthCare 226 West. 227 228 d. Clinics will be trained to use the tools.

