#### 323 324 **1.9 Maintenance**

The second year of the intervention will be considered a maintenance year. Maintenance will comprise the following activities:

327 328

329

330

331

- Health Center leaders will choose whether to maintain the program in YRO2 at the intervention sites;
- Those that maintain will document any adaptations that they make to the program, and we will capture this during the qualitative Rapid Assessment Process (See Section 2.8)
- Health Center leaders will also choose whether to roll-out the program in YR02 to usual care clinics within their health center.
  - Health Center leaders may also opt to roll-out the program in YR02 to additional clinics in their health center that did not participate in the study (neither intervention or usual care).
- 335 336

334

The research team will document maintenance at the clinic- and patient-levels. Clinic-level maintenance
will assess the number of clinics that maintained the program in Year 02, overall and by intervention status
(including clinics that were neither assigned to intervention or usual care). Patient-level maintenance will
assess the proportion of patients who completed fecal testing in both years of the program.

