## 486 **2.3 Study Outcomes**

487 The original UH3 protocol stated that the study population would be accrued over the 12 months following

randomization (February 4, 2014–February 3, 2015) and then be followed for 12 months after that to assess

489 the study outcome. However due to the decision to roll out the intervention to control clinics in August of

2015, we truncated the follow up window for all individuals, intervention and control, as of this date. In
addition, delays in intervention startup required us to reformulate some of our secondary outcomes. The

- 491 addition, delays in intervention startup required us to reformulate some of our second.
- 492 revised is a statement of our current primary and secondary outcomes.

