## 505 2.3.2 Secondary Outcomes

[figure not shown]
- 506 Our secondary outcomes are provided below:
- For participants who received a FIT kit, the probability of returning it within 3, 6, 9 and 12 months of its being sent as well as time to FIT/FOBT return
   Receipt of any CRC screening (fecal test, sigmoidoscopy or colonoscopy) during the follow-
  - NQF score (proportion of those age 50-74 with a colonoscopy within 10 years, flexible
  - sigmoidoscopy within 5 years, and FOBT/FIT within 1 year) as assessed relative to the oneyear pre and each of the first two years post randomization
    - Presence of a positive FIT/FOBT among those who return a FIT kit
    - Referral for a colonoscopy among those with a positive FIT/FOBT
    - Completion of a colonoscopy following a positive FIT/FOBT

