### 637 Secondary Analyses

638 We used the same analytic approach for the secondary outcome of any CRC screening. For both FIT

- 639 completion and any CRC screening, additional models were fit using interaction terms to test the extent to
- which the intervention effect differed across Health Centers. The interactions were treated as fixed effectsin these models.
- 642

643 The analysis of our other secondary outcomes will be more descriptive in nature. Regarding the proportion 644 of returned FOBT/FIT kits that turn out positive, while we anticipate a sizeable number of returned 645 FOBT/FIT kits for each of the intervention clinic (typically in excess of 150), the numbers will be much 646 smaller for control clinics (for many of the smaller clinics less than 20) and hence much less precisely 647 measured. The situation is only compounded for the secondary outcomes of referral for a positive FIT and 648 completion of a colonoscopy following referral, since they are further limited to FOBT/FIT kits that are 649 returned and are positive. Hence, for all these outcomes, the focus will be more on the experience of the 650 intervention clinics than formal comparisons between intervention and control clinics, though we will look 651 at this latter question to the extent we are able. Ultimately, we wish to know the extent to which the 652 clinics are able to maintain the program and the impact it may have on their operations, and hope that this 653 information will help to shed light on this issue.

654

For the NQF scores, the data can be interpreted as coming from a step wedge design. In the year prior to
randomization all clinics were following usual care. In the first-year post randomization the intervention
clinics were using the intervention and the control clinics still usual care. In the second-year post
intervention all clinics were using the intervention. In each case we have a single observation per clinic.

659 We will use a random effects model to assess intervention effects while adjusting for within clinic

- 660 clustering. The model will allow for period effects and will also estimate separate effects for the first and
- 661 second year of intervention rollout.
- 662
- 663 Sensitivity Analyses

664 Sensitivity analysis will include GEE models without weighting, GEE models that also adjust for insurance 665 status, random effects models, and models excluding the two clinics (one intervention and one control)

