- 666 affiliated with an academic medical center (these clinics did not have shared governance and did not use 667 the same FIT kit throughout the intervention).
- 668

669 Finally, while our primary analysis will include all individuals accrued after EHR tools were provided to

670 clinics on February 4, 2014, no clinic began printing letters until at least June of 2014; some did not begin

671 until spring of 2015. To account for this implementation delay, we will repeat the above analyses for FIT

- 672 completion and "any CRC screening" using a lagged dataset that only included individuals accrued between
- 573 June 4, 2014 and February 3, 2015. As with the primary dataset, outcomes for this lagged dataset will be
- assessed through August 3, 2015, after which materials were made available to usual care clinics.
- 675

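### The NQF stepped-wedge model assumes full-year exposure that the protocol's own start and roll-out dates contradict: the first-year effect is diluted and the second-year effect is biased in an unknown direction

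*Protocol*

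**What the plan says.** Section 2.3.2 lists the NQF score as a secondary outcome, assessed for the year before randomization and "each of the first two years post randomization". Section 2.4.1 (Secondary Analyses) reads these data as a stepped wedge. In year 1 the intervention "clinics were using the intervention and the control clinics still usual care"; for the second year post "intervention all clinics were using the intervention. In each case we have a single observation per clinic". The analysis is a random effects model: "The model will allow for period effects and will also estimate separate effects for the first and" second year of rollout.

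Other sections describe the calendar differently:

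- Section 2.2 dates randomization to 4 February 2014, and Section 2.3 gives the 12 months following "randomization (February 4, 2014–February 3, 2015) and then be followed for 12 months after that to assess" the outcome. Year 1 is thus 4 February 2014 to 3 February 2015, and year 2 is 4 February 2015 to 3 February 2016.
- Section 2.4.1 (Sensitivity Analyses): "no clinic began printing letters until at least June of 2014; some did not begin" until spring 2015.
- Section 1.5.1: "Usual care clinics will have access to the STOP CRC tools on a delayed roll-out beginning" August 2015. Section 2.3.1 gives the date as 3 August 2015.
- Section 1.9: "Health Center leaders will also choose whether to roll-out the program in YR02 to usual care" clinics. The same section leaves maintenance at intervention clinics to health center leaders, and Section 2.3.4 plans to track clinics that decline in year 2.

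The lagged analysis added for start-up delay covers FIT completion and any CRC screening. It does not cover the NQF score.

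**The concern.** Once every clinic is coded as exposed in year 2, that year has no unexposed comparator. The model can then separate the second-year effect from the year-2 period effect only by assuming that usual care clinics, in their first rollout year, show the same effect that intervention clinics showed in theirs. The protocol's dates give no reason to expect this. Intervention clinics had part of year 1, by differing amounts; usual care clinics had at most about half of year 2, and only where their health center chose to take the program up. Any mismatch passes directly into the second-year estimate, which is the figure a reader would take as evidence that the program's effect is sustained. The first-year estimate has a simpler problem: it describes a partly implemented year but is presented as a year of use.

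**Working it through.** The protocol gives no figure for this analysis, so there is none to reproduce.

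**Identification.** Index the effects by time since a clinic's own rollout: θ1 for its first year, θ2 for its second. With baseline mean μ and period effects π1 and π2, the model's expected means are:

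| Arm | Pre-year | Year 1 | Year 2 |
|---|---|---|---|
| Intervention | μ | μ + π1 + θ1 | μ + π2 + θ2 |
| Usual care | μ | μ + π1 | μ + π2 + θ1 |

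Writing I and C for the arm means, I1 − C1 = θ1 and I2 − C2 = θ2 − θ1. Hence θ2 = (I2 − C2) + (I1 − C1).

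**Bias, with no dose assumption.** Let a be the intervention clinics' actual year-1 effect, e their actual year-2 effect, and b the usual care clinics' actual year-2 effect. The expected estimate of θ2 is (e − b) + a, so its bias relative to e is a − b. It is zero only if a = b.

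**Exposure limits from the dates.**

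- g, intervention clinics in year 1: the earliest start is June 2014. From 1 June 2014 to 3 February 2015 is 248 days, and 248/365 = 0.68. Clinics starting in spring 2015 have g = 0.
- f, usual care clinics in year 2: from 3 August 2015 to 3 February 2016 is 185 days, and 185/365 = 0.51. Clinics that do not roll out have f = 0.
- m, intervention clinics in year 2: at most 1, because maintenance is optional.

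No distribution of start dates, uptake or maintenance is given.

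**Size, under added assumptions.** Assume that the effect is proportional to the fraction of the year exposed and that the full-year effect d is the same in both years. Then E[θ1] = g·d, at most 0.68d, and E[θ2] = d(g + m − f).

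| g | f | m | E[θ2]/d |
|---|---|---|---|
| 1 | 1 | 1 | 1.00 (as the model assumes) |
| 0.68 | 0 | 1 | 1.68 |
| 0.68 | 0.25 | 1 | 1.43 |
| 0.68 | 0.51 | 1 | 1.17 |
| 0.50 | 0.50 | 1 | 1.00 |
| 0.33 | 0.50 | 1 | 0.83 |
| 0 | 0.51 | 1 | 0.49 |
| 0.68 | 0 | 0.5 | 1.18 |
| 0.68 | 0.51 | 0.5 | 0.67 |

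A generalized least squares calculation with a random clinic intercept and 13 clinics per arm (assumed) gave the same values at within-clinic correlations of 0.2 and 0.8.

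**An alternative reading.** If the separate effects refer to calendar years, the year-2 term applies to every clinic and is collinear with the year-2 period effect. The design matrix then has rank 4 for 5 parameters, and the second-year effect cannot be estimated.

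**The case against.** The best defense is that the model does not need full-year exposure. It needs only the same first-rollout-year effect in both arms, and two similarly partial first years cancel, as the row with g = f = 0.50 shows. That is correct, and it is why the direction is not fixed. But the protocol gives no basis for equality: the two arms have different calendar limits, and year-2 uptake was a choice.

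Proportional scaling can also be questioned. The NQF score looks back 1, 5 or 10 years depending on the test, and Section 1.14 lets clinics mail by birth month or less often, so a clinic mailing in batches could reach most of its due patients quickly. This weakens the multiples in the table but not the expression a − b.

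A reader might infer that the second-year effect is necessarily overstated, by up to two thirds. The documents do not support that. The figure needs no usual care roll-out at all, whereas Section 2.3 records a decision to roll out in August 2015 and Section 2.7 lists observation of control clinic roll-out trainings for summer 2015. It needs every intervention clinic to have started in June 2014, which Section 2.4.1 denies. It also needs full maintenance and a linear dose. One can argue for upward bias by giving both arms the same lag from tool access to first letter: with 4 months, g = 8/12 = 0.67, f = 2/12 = 0.17, and the ratio is 0.67 + 1 − 0.17 = 1.50. But equal lag is an assumption. Section 1.5.1 shows that clinics waited for an EPIC upgrade in 2014, so usual care clinics could have started faster in 2015.

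**Conclusion.** Wrong as written, moderate severity. The statement that all clinics were using the intervention in year 2 conflicts with Sections 1.5.1, 1.9 and 2.3.1, and the year-1 description conflicts with the start dates given under Sensitivity Analyses. The first-year NQF effect is diluted, to at most about 0.68 of a full-year effect if effect scales with exposure time. The second-year effect is biased by a − b, with sign and size set by actual start dates. The range of about 0.5 to 1.7 times the full-year effect rests on proportional exposure, equal yearly effects and full maintenance. Both ends are corner cases: the lower end needs every intervention clinic to have started after year 1, while the protocol says only that some did. Non-maintenance would lower the estimate further relative to a full-year effect.

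The damage is confined to one secondary outcome. The primary outcome and its follow-up end no later than 3 August 2015, before usual care clinics had the tools. The year-1 NQF contrast is likewise free of usual care roll-out; it needs only an accurate description.

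**What to change.** 1. In Section 2.4.1, replace the statement about year 2 with the actual position: tools available to usual care clinics from August 2015, roll-out and maintenance optional. Describe year 1 with its real start dates.
2. Make the randomized year-1 comparison, adjusted for each clinic's pre-randomization NQF score, the NQF effectiveness result. Describe it as the effect of assignment with delayed start-up.
3. Present any second-year estimate as descriptive and not protected by randomization. State that the two effects are indexed by time since a clinic's own rollout, so that the model is identifiable.
4. If the three-period model is kept, add a sensitivity analysis that codes each clinic-year, in both arms and both years, by the fraction of the year exposed from actual start dates. Label it as-treated, because uptake was chosen after randomization; for that reason it should not replace the main result.
5. Extend the start-up-delay sensitivity analysis to the NQF score.

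Moving the annual cut points to August is not a remedy. It would put randomization, and letters mailed from June 2014, inside the baseline year.

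The cost is mainly wording. The EHR data are held, and Section 2.3.3 already captures letter-mailing dates in Reporting Workbench. The price is a less precise and more cautious second-year estimate.

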## 676 2.4.2 Analysis of Process Data

We will use proportions of clinics or patients to calculate adoption, reach, implementation and
maintenance. Consistent with our adapted CONSORT, to the extent possible, we will report descriptive
characteristics of adopters vs. non-adopters and maintainers vs. non-maintainers (at the clinic level) and
completers vs. non-completers in YRS 01-02 (at the patient level).

681

## 682 2.4.3 Moderator analysis

In addition to the previously mentioned analysis looking at whether the intervention effect varied by
service area network, we plan to conduct a detailed moderator analysis looking at the extent to which the
intervention effects persisted within, and potentially differ across, subgroups defined by a variety of patient
level factors. Since the focus of these analysis is on patient level effects, we will use random effects, rather
than GEE models, for these analyses.

688 689

702

## 690 **2.5. Power and Sample Size**

For Phase 2, STOP effectiveness will be assessed using a two-arm, cluster randomized design with a total of26 clinics. Our power calculations are based on the following assumptions:

- We have equal Ns per clinic and equal numbers of clinics per group. In practice, the sample sizes will not be equal, but since almost all clinics had at least 450 subjects who qualified for the intervention (most had at least 700 qualifying individuals), we conservatively use this figure for all sites.
- We compare two binomial proportions with a type I error rate of 5%. For each of a variety of
   design assumptions, we determined the design effect due to clustering and used this to calculate
   the effective sample size as if these were independent observations. We then used the formulas
   from Hulley et al., to estimate power.
- Finally, we assume an intention-to-treat approach in which we consider a treatment failure to be any individual who receives the initial intervention mailing (or for the UC clinics would have qualified to receive the mailing) and does not have a completed fecal test within their follow-up window. Although we expect to learn through the intervention process that many intervention participants do not require screening, we have no way to exclude comparable individuals from the control clinics and hence must ignore this information for the primary analysis.
- 709
  710 We calculated power for Intra-class Correlation Coefficients (ICCs) of .03, .04, and .05, usual care FIT return
  711 probabilities of 5%, 10%, and 15%, and intervention effects (absolute differences) of 10 14 percentage

- points. Based on analyses done by [name] (STOP co-PI), we expected the ICC to be about .03, though as
  it turned out the ICC was closer to .05. Using this latter figure, we had >90% power for detecting effect
  sizes of at least 13 percentage points even with UC probabilities as high as 15%. Power was > 88% for
  detecting effect sizes of at least 11 percentage points if the UC probabilities were no higher than 10%.
  Power declines only slightly even for subgroups 1/6th of the full cohort (e.g., for 17% Hispanic patients).
- 717 This reflects the fact that we have an overabundance of individuals within each clinic and that the main
- 718 driver of power is thus the number of clinics.
- 719

## 720 Estimated Power with 26 clinics

721

			Difference in probability between intervention and UC					
	ICC=.03		.10	.11	.12	.13	.14	
		.05	99.2%	99.7%	99.9%	99.9%	100.0%	
	Prob in UC	.10	96.2%	98.1%	99.1%	99.6%	99.8%	
		.15	91.7%	95.4%	97.6%	98.8%	99.4%	
722								
723								
	ICC=.04		.10	.11	.12	.13	.14	
		.05	97.1%	98.5%	99.3%	99.7%	99.8%	
	Prob in UC	.10	90.2%	94.2%	96.7%	98.2%	99.1%	
		.15	82.6%	88.7%	93.0%	95.8%	97.6%	
724 725								
	ICC=.05		.10	.11	.12	.13	.14	
		.05	93.2%	96.1%	97.8%	98.8%	99.4%	
	Prob in UC	.10	82.6%	88.5%	92.7%	95.5%	97.3%	
		.15	73.2%	80.7%	86.7%	91.1%	94.3%	

- 726
- 727
- 728
- 729

### 730 2.6. Cost Analysis

Our cost analysis will assess the costs and long-term cost-effectiveness of the Enhanced Auto Intervention,
 relative to usual care. The second primary outcome is an analysis of the cost, cost-effectiveness, and return
 on investment. The goal of cost-effectiveness analysis is to select the strategy that yields the greatest
 incremental health benefits per additional dollar spent.

736 Incremental cost-effectiveness: The measure of promotion success is how many members of the eligible
 737 population obtain screening. The difference in cost over the difference in effectiveness of a new
 738 intervention vs. standard care is the incremental cost-effectiveness of the new intervention, derived as:
 739

740 741

Incremental Cost-Effectiveness New = (CNew – CStd )/(ENew – EStd)

where CNew and CStd refer to average total costs, and ENew and EStd refer to average total effectiveness

- for the new and standard arms, respectively. We denote the total cost of screening as Csceen. Screening
- promotion programs also have a per-person denoted as Cpromote. By reducing the incidence of advanced

745 cancers, screening can reduce the cost of treating cancer in those who were destined to develop the 746 disease, denoted as Ccancer. Total costs for a particular screening + promotion program A are: 747 748 CA = [CsceenA + CpromoteA - CcancerA ] 749 750 751 By reducing the incidence of advanced cancers, screening technologies increase the number of life years 752 (LY) for a population, less any morbid or mortal side effects of the screening intervention. Thus, in 753 comparing two screening promotion programs, the incremental cost-effectiveness of new program A versus 754 the established program B is: 755 756 Incremental Cost-Effectiveness Program A = (CA – CB)/(LYA – LYB) 757 758 We will report cost-effectiveness as cost per additional screenee and cost per LY gained (note that cost per 759 additional screenee does not include CsceenA or CcancerA and the denominator is total number of persons 760 in each population obtaining screening rather than LY). Since realization of the benefits of screening 761 promotion programs will take years or even decades, direct evaluation of the impact of promotion from the 762 trial on LY is infeasible. 763 764 Costs associated with promotion (Cpromotion): We will document the non-research costs associated with 765 implementing the CRC screening intervention. These include associated fixed costs (i.e., those unrelated to 766 the size of the target group) and variable costs. Fixed costs include implementation costs (e.g., staff 767 training), maintenance, office space used in the clinic, equipment and materials (e.g., computers), and 768 telephone. Variable costs include labor costs associated with delivering the interventions as well as 769 materials distributed to the participants (e.g., FITs). Accounting systems will be used as a source of data on 770 the cost of equipment and supplies (e.g., printing). To estimate labor costs associated with delivering the 771 intervention, clinic staff will record the time they spend delivering intervention components (e.g., for 772 placing FIT orders) on staff logs. Fixed and variable costs will be amortized to determine the average 773 expenditure associated with delivering an intervention (e.g., mailing costs) to the study population 774 (Cpromotion). 775 776 **Costs of colorectal cancer screening (Cscreen).** Each individual who obtains screening will be assigned an 777 associated cost, including the time-costs associated with screening, and costs for evaluation of true and 778 false positives. Test and evaluation costs will be based on reimbursements from nationally standardized 779 databases (e.g., Medicare reimbursements). As this is a home-based test, no time will be associated with 780 transportation. Time spent in screening will be valued by national wage rates for individuals of the study 781 population's age group and ethnicity. (This time is anticipated to be low.) 782 783 Estimating LY gained and quality-adjusted LY. Our trial is not designed to estimate differences in CRC rates 784 or survival for the screened population. These will need to be estimated through modeling. We propose 785 building a Markov state transition model to estimate years of life gained and quality-adjusted LY. Three 786 states are accounted for: healthy, CRC, and death. The healthy and CRC states are assigned a utility weight 787 for calculating quality-adjusted LY are calculated. 788 We start with simplifying assumptions that all individuals who start screening as a result of the program will 789 continue and those who screen have no risk for developing invasive CRC. Risk of death in each year will be 790 determined from life tables; risk of CRC in the unscreened population will be based on epidemiological 791 data. Those who develop CRC face a risk of death (from other causes) or death from CRC. Disease-specific 792 survival rates for CRC will be based on Surveillance Epidemiology and End Results (SEER) survival data.(3). A-25

- 793 Consistent with previous research, we will use a three percent annual rate for discounting future costs and 794 LY after conversion of all costs to a constant year's dollars. We will conduct one-way and multiway
- residual sensitivity analyses to explore the robustness of cost-effectiveness ratios to changes in assumptions.
- 796

**Return on investment.** Following the AHRQ Health Care Exchange recommendations, we will also present results in an ROI format. ROI can be measured prospectively or retrospectively and has historically been defined as the amount an organization expects to save (i.e., the difference in healthcare expenditures with and without a specified program), compared to expected program costs. Although results are sometimes reported as a ratio (e.g., ROI = savings/program costs, in current dollars), ratios are subject to misleading scale effects. The preferred financial metric is "net present value" (i.e., savings less program costs, in current dollars). In this sense, an ROI analysis is a restricted cost-benefit analysis.

804

812

805 Learning from Phase 1: Our Phase 1 experience will inform the Phase 2 economic evaluation, using the 806 following analytic plan. One objective of the economic evaluation is to categorize program labor costs by 807 both individual and by activity. In particular, we will refine our data collection methods, particularly as they 808 can greatly influence our understanding of the multiple program tasks a given individual may perform. We 809 will consult with the project team to appropriately categorize activities to be tracked and over what time 810 frame. Below is the sample data capture sheet for ongoing intervention time, centralized outreach and 811 management functions.

- 813 Mailing work associated with mailing letters, FIT Kits and post cards
- 814 **Prep time** work associated with planning and organizing the mailings
- 815 **Clinic staff meetings, PDSA and training work** work associated with clinic meeting and training 816 time to launch and improve the intervention
- 817 EMR changes work associated with requesting, specifying, testing and implementing EMR
- 818 changes associated with the intervention
- Administration time work associated with organizing meetings and logistics, preparing and
   distributing meeting materials and minutes associated with the intervention.
- 821 Project consultation meetings work associated with meetings of clinic staff with research project
   822 staff and/or OCHIN staff
- 823Other other work related to ongoing delivery of the intervention but not associated with above824categories
- 825

